3.6.5.3 Controlled assessment period treatment completion

A treatment completer for the controlled assessment period is defined as a patient who has a Week 24 assessment without discontinuing study medication for the controlled assessment period prior to the visit.

3.6.5.4 Controlled assessment period completion

A completer of the controlled assessment period is defined as a patient who has a Week 24 assessment regardless of study medication status at the visit.

3.6.5.5 Extension period treatment completion

A treatment completer for the extension period is defined as a patient who has a Week 52 assessment without discontinuing open-label EQW for the extension period prior to the visit.

3.6.5.6 Extension period completion

A completer of the extension period is defined as a patient who has a Week 52 assessment regardless of open-label EQW status at the visit.

3.6.6 Total daily insulin dose

Baseline total daily insulin dose will be calculated as the sum of available insulin doses taken in the 7 days prior to date of first dose of randomized study treatment, divided by 7. This is because it is not possible to ascertain whether insulin taken on date of first study treatment was pre or post dose.

Total daily dose for all post-baseline visits to Week 52 will be calculated as the sum of available insulin doses taken 6 days before and additionally including the target day of each visit (e.g. Week 4 total daily dose will be based on insulin taken on study day 29, plus the 6 days prior), divided by 7. If a subject is missing days with insulin records within the range, total daily dose will be set to zero for that day (i.e. absence of insulin implies the patient was

not taking insulin). For the Week 24 visit only, total daily dose will be calculated as 7 days prior to the Week 24 visit, divided by 7.

Overlapping records for short-acting insulin medications (i.e. multiple insulin records known to be received on the same day) will be summed to obtain the total daily dose on that day. Overlapping records for long-acting insulin medications will be queried to site. Where overlapping records of one day still occur, it will be assumed the new long-acting insulin dose started the day after the current long-acting insulin dose.

Only records with dose in units (IU) will be included in the derivation of total daily dose. Any medications identified as “Intermediate” will be classified under short-acting insulin medications.

For the purposes of derivation of total daily insulin dose, insulin records with completely missing start dates will have start date imputed as 7 days prior to first dose of randomized study treatment, except in the case where stop date of the medication is earlier than 7 days before first dose. Completely missing end dates will be imputed as date of last contact. Partial start and end dates will be imputed using the rules in Section 7.2.

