3.6.4 Rescue therapy

Rescue therapy is defined as any new concomitant medication (see Section 4.2.1.4 for detail) with therapy reason given as “Protocol defined exacerbation of disease under study”.

A rescue episode will be defined as the first unique rescue therapy entry on the CM eCRF. If a patient has multiple entries on the CM form flagged as a rescue therapy, the first will be considered the point at which the patient was rescued.

Increases in insulin from baseline in patients receiving insulin at baseline will be programmatically derived from the CM CRF and reviewed by the clinical team prior to unblinding. Increases identified as potential rescue episodes will be queried at the site-level and therapy reason may be updated to “Protocol defined exacerbation of disease under study”.

For patients who require initiation of rescue therapy and continue study treatment, only data before initiation of rescue therapy will be included in the primary efficacy analysis. If HbA1c is measured before rescue therapy, then we will include the HbA1c measurement. If HbA1c is measured on the date of first rescue therapy but no time information is available to indicate if it was taken before rescue therapy, then HbA1c will be assumed to be prior and included in the primary efficacy analysis. Sensitivity analyses including data after initiation of rescue therapy will be carried out to test the robustness of the missing data assumption.

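### SAP 3.6.6 can understate total daily insulin, down to zero, when a record has no usable IU dose, and can add old and new short-acting doses when change dates are imputed

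*SAP*

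**What the plan says.** SAP 3.6.6 defines baseline total daily insulin as the "sum of available insulin doses taken in the 7 days prior to date of first dose of randomized study treatment, divided by 7". Post-baseline visits use the same divisor over a seven-day window, set out in Table 3.4.

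Four further rules in 3.6.6 matter here:

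- **Unit filter.** "Only records with dose in units (IU) will be included in the derivation of total daily dose".
- **Zero rule.** "If a subject is missing days with insulin records within the range, total daily dose will be set to zero for that day". The reason given is that "absence of insulin implies the patient was" not on insulin.
- **Overlaps.** Short-acting records that overlap "will be summed to obtain the total daily dose on that day". A parenthesis describes these as records known to apply to the same day. Intermediate insulin is classed with short-acting. Long-acting overlaps go to the site as a query, and a remaining one-day overlap is resolved by starting the new dose a day later.
- **Dates.** "Partial start and end dates will be imputed using the rules in Section 7.2". Section 7.2 (Appendix B2) takes the earliest possible start and the latest possible stop. A completely missing end date becomes the date of last contact.

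SAP 4.2.1.4 uses the result to summarize background insulin as long-acting, short-acting and overall dose.

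**The concern.** The zero rule rests on the idea that no record means no insulin. That reasoning does not cover a day with an insulin record whose dose is blank or in another unit: use is documented and only the amount is unknown. Section 3.6.6 does not address this day. Applied as written, it contributes nothing while still counting in the divisor.

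The date rules cause a separate difficulty in the other direction. Section 7.2 was written to classify medications as pre-treatment, prior or new concomitant, and wide imputed intervals serve that purpose. Used for dose totals, the same intervals can create overlap between a dose that ended and the dose that replaced it.

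Protocol 5.6 asks that insulin stay constant as far as possible but allows changes to limit hypoglycemia. The insulin summary is therefore where a reader checks whether an HbA1c difference came with a change in insulin. A false low dose looks like insulin sparing, and a false sum looks like intensification.

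**Working it through.** The plan states no figure that depends on this rule, so there is none to reproduce. The check applies the rules of 3.6.6 and 7.2 to assumed records. The Table 3.4 windows confirm the divisor: days -7 to -1 and days 23 to 29 are seven days each.

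**1. Days with a record but no usable IU dose**

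Assume a true dose of 40 IU/day and *k* such days in the window. The reported average is (7 - k) × 40 / 7.

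| k | Calculation | Reported, IU/day |
|---|---|---|
| 0 | 7 × 40 / 7 | 40.0 |
| 1 | 6 × 40 / 7 | 34.3 |
| 3 | 4 × 40 / 7 | 22.9 |
| 6 | 1 × 40 / 7 | 5.7 |
| 7 | 0 / 7 | 0.0 |

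If those days were missing and left out of the divisor, the average would stay at 40.0 for k = 1 to 6 and be missing for k = 7.

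The result is exactly zero only if no other IU record covers the window. With 30 IU of long-acting insulin recorded and a short-acting record lacking an IU dose, the overall total is 30: understated, but not zero. The short-acting component is 0.

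**2. Overlap created by date imputation (short-acting and intermediate)**

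Assume a dose change in May, with the old stop and the new start both known only to the month. Section 7.2 ends the old record on 31 May and starts the new one on 1 May, so they overlap for 31 days. If that overlap is summed, a seven-day window inside May gives:

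| Old to new, IU | Reported | Truth | Ratio |
|---|---|---|---|
| 20 to 20 | 20 + 20 = 40 | 20 | 2.00 |
| 20 to 24 | 20 + 24 = 44 | 20 to 24 | 44/24 = 1.83 to 44/20 = 2.20 |
| 20 to 10 | 20 + 10 = 30 | 10 to 20 | 30/20 = 1.50 to 30/10 = 3.00 |

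The range in the truth reflects whether the change came after or before the window.

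If only one of the two dates is partial, the ratio runs from 1.00 up to the same maxima. For example, take a window of 11 to 17 May and a change from 20 to 24 IU on 15 May. The truth is (4 × 20 + 3 × 24) / 7 = 21.7. With only the stop partial, the result is (4 × 20 + 3 × 44) / 7 = 30.3, a ratio of 1.39. With only the start partial, it is (4 × 44 + 3 × 24) / 7 = 35.4, a ratio of 1.63.

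**3. Where the error can appear**

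The dose is computed only in the Table 3.4 windows. From Week 28 the target days are nominally 197, 281 and 365, which are 12 weeks apart, so an overlap of one month may touch no window. An old short-acting record with a completely missing end date is different: it runs to last contact and overlaps every later record.

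**The case against.** The strongest reply is that 3.6.6 does not actually prescribe these errors. It sets zero for days without insulin records and is silent on days with a record but no IU dose. It limits summing to records known to fall on the same day, and an imputed overlap is not known. Long-acting overlaps are queried. Protocol 5.6 requires regimen changes to be reported to the sponsor, and Protocol Section 10 provides for queries on missing or inconsistent data, so such records should be few. A user with a false zero still appears in the antidiabetic medication table of SAP 4.2.1.4, which does not depend on dose.

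Much of this stands. The false sum depends on how *known* is read, and it does not apply to long-acting insulin, where the gap is only a missing rule for overlaps longer than one day. The understatement is less open to interpretation: the unit filter, the sum of available doses and the fixed divisor together produce it unless a programmer adds a rule.

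A reader might infer that insulin use will generally be reported as zero or doubled. The documents do not support that. Zero needs a whole window without any IU record, and exact doubling needs equal doses and full overlap.

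A reader might also infer that rescue identification is compromised. SAP 3.6.4 says "Increases in insulin from baseline in patients receiving insulin at baseline will be programmatically derived from the CM CRF". It does not mention the 3.6.6 average, and it adds clinical review before unblinding and site queries.

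**Conclusion.** The point holds as a limited defect in a descriptive derivation. For a patient with a documented insulin record but no usable IU dose, total daily insulin can be understated by one seventh of the true dose per affected day, down to zero. For short-acting and intermediate insulin, if imputed overlap is treated as same-day use, the value in an affected window can be inflated by a factor between 1 and 3 in the examples worked.

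All doses and dates above are assumptions. The documents give no rate of non-IU records or partial dates, so the effect on arm-level summaries cannot be sized. The variable is not an endpoint, is not in the testing hierarchy and does not enter the primary MMRM. Nothing here bears on the primary result; the consequence is for how the background-insulin summary is read beside it.

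**What to change.** Amend SAP 3.6.6 in two places.

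1. **Unusable dose.** Where an insulin record covers a day but has no usable IU dose, set that day to missing for the affected insulin class and for the overall total, and keep valid doses of the other class. Average over the remaining days. Report the visit as missing if too few days remain, with the minimum set by the sponsor before unblinding. Use zero only when no insulin record of any kind covers the day. The SAP already accepts an uncalculated visit: the note under Table 3.4 does so when study medication stops before the window closes.

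2. **Imputed overlap.** Where consecutive records of the same product overlap only because a date was imputed, end the earlier record the day before the later one starts. If the earlier stop is complete and only the later start was imputed, move that start to the day after the stop, so that a known date is not overridden. Continue to sum records with known dates that are truly concurrent, such as two mealtime doses of one product.

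With both dates partial, the assumed change from 20 to 24 IU would then give 24 throughout May, at most 24/20 = 1.20 times the truth instead of 2.20.

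The cross-reference in SAP 4.2.1.4 should also point to 3.6.6; it now cites 3.6.5.

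The cost is SAP wording and minor programming, and a few visits become missing instead of zero.

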3.6.7 Free testosterone

Free testosterone will be derived at each visit using the following equations steps:

$N = 1 + \text{Kalb} * \text{ALB} / 69000$
$a = N * \text{Kshbg}$
$b = N + \text{Kshbg} * (\text{SHBG} - \text{TT}) / 10^9$
$c = -\text{TT} / 10^9$
$\text{FT} = (-b + \sqrt{b^2 - 4 * a * c}) / (2 * a) * 10^9$

Where,

- Kalb is constant for albumin, defined as 3.6×10^4
- Kshbg is constant for SHBG, defined as 10^9
- ALB is albumin in g/L
- SHBG is sex hormone binding globulin in nmol/L
- TT is total testosterone in nmol/L
- FT is free testosterone

4. ANALYSIS METHODS

4.1 General principles

All statistical evaluations as well as summaries and tabulations will be done by qualified personnel at IQVIA. Before breaking the treatment codes, following clean file declaration (database lock), all decisions on the evaluability of the data for each individual patient will be made and documented, and each patient will be assigned to the appropriate analysis set.

Statistical analysis software (SAS) version 9.4 or later will be used to generate all statistical analyses, data summaries and listing.

4.1.1 Statistical notations and presentations

In general, all efficacy and safety variables will be summarized using descriptive statistics as appropriate. Continuous variables will be summarized by descriptive statistics (sample size (n), mean, SD, minimum, median and maximum). Quartiles 1 and 3 may be included for some parameters where appropriate. The mean and median will be presented with one more decimal place than the original data. Standard deviation with two more decimal places than the original data. Minimum and maximum values with the same number of decimal places than the original data. Categorical variables will be summarized using frequency tables (frequencies and percentages). Percentages will be rounded to 1 decimal place.

For log-transformed data, the following descriptive statistics will be presented: n, geometric mean, geometric coefficient of variation (GCV%), geometric standard deviation factor (GSD), arithmetic mean, standard deviation, coefficient of variation (CV%), median, minimum and maximum.

GCV (%) will be calculated as

$$100 \cdot \sqrt{(\exp(s^2) - 1)}$$

where s is the SD of the data on a log scale.

Individual data will be presented in patient listings. All patient data listings will be sorted by treatment and patient ID.

In outputs, the following treatment labels will be used, except where data from the extension period are displayed:

Treatment group	Label
Exenatide 2mg	EQW
Placebo	Placebo

Summaries including data from the extension period will be presented by the controlled assessment period treatment group. The following treatment labels will be used:

Treatment group during controlled assessment period	Label
Exenatide 2mg	EQW
Placebo	Placebo -> EQW

4.1.2 Hypothesis testing significance level

All statistical tests will be conducted at a 2-sided significance level of 5% unless otherwise specified. Where appropriate, model-based point estimates, together with their 95% confidence intervals will be presented along with the 2-sided p-values for the tests. P-values will be rounded to 3 decimal places.

A hierarchy of the primary and selected secondary endpoints is defined in Section 4.2.3.2.

4.1.3 Handling of missing data

4.1.3.1 Missing efficacy data

Missing data in this study may result from patients discontinuing from the study prematurely or missing intermediate visits or selected assessments while remaining on study. Every effort will be made to obtain the CSP-required data for all study assessments that are scheduled for all patients who have been enrolled. Data collected after initiation of rescue therapy will be excluded from most efficacy analyses (see Section 4.2.3 for details) and therefore these data will effectively be handled as missing in analyses. For efficacy analyses, in general missing observations will not be imputed, except those inherited from the mixed model repeated measures (MMRM) which implicitly assumes that data are missing at random (MAR). A sensitivity for the primary analysis will be performed using pattern mixture model imputation for missing values and details of this imputation is provided in Section 4.2.3.4.

Missing at Random (MAR) refers to missingness that is independent of missing responses, conditionally on observed responses and covariates. As the imputation strategy should always consider the dropout patterns and the time-course of the efficacy measurements by treatment, the pre- and post- withdrawal values will be assessed to understand the impact of dropouts on the efficacy results. The primary efficacy endpoint of HbA1c data will be visually examined to explore the missingness patterns by (1) plotting each individual patient's HbA1c change trajectory in completers side-by-side with those who have prematurely discontinued study medication, and by (2) plotting the last HbA1c change from baseline for those who discontinue study medication prematurely, overlaid with the box plot of change from baseline in HbA1c by visit for completers.

For categorical endpoints HbA1c goals of $<6.5\%$, $\leq 6.5\%$ and $< 7\%$ at 24 weeks, any patient with missing HbA1c value at 24 weeks will be considered as failed to meet HbA1c $<6.5\%$, $\leq 6.5\%$ and $< 7\%$, respectively, at endpoint (24 Weeks). The same will apply for these endpoints at 52 weeks endpoint.

4.1.3.2 Missing baseline and demographic data

For demographic and baseline characteristics, each variable will be analyzed and/or summarized using the available data. For continuous variables, missing data will be indicated in the "n" count and for categorical variables, unless indicated otherwise, percentages will be calculated out of the total number of patients with data available. A count of patients with missing data will be tabulated.

4.1.3.3 Missing safety data

Safety analyses will be conducted on the observed data only.

However, imputation of missing or partial AE and concomitant medication onset/start and end/stop dates will be used to determine the status of each AE and the previous/concomitant status of each medication. Refer to [Appendix B1](#) and [B2](#) for the method of imputation of missing/partial AE/concomitant onset/start and end/stop dates. Missing/partial start/stop dates will appear as is (i.e., without imputation) in the patient data listings, but will be imputed to permit the proper tabulation of AE and concomitant medications data.

4.1.3.4 Premature discontinuation

Patients who discontinue study medication prior to Visit 11 (Week 62/Study Termination) should enter the Extended Safety Follow-up Period, unless they have a height difference of less than 5 mm over a 6-month interval at study-site visits prior to discontinuation of study medication. Efficacy data are not collected during the Extended Safety Follow-up Period and this period will be reported separately to the primary clinical study report (CSR), so data beyond discontinuation of study medication will not be included in analyses.

Patients who discontinue the study prematurely should have all early termination visit procedures done at the time of study discontinuation.

4.1.4 Handling of data post rescue medication

Instances of patients meeting rescue criteria and subsequently receiving rescue medication will be recorded by sites as defined in Section 3.6.3.

A loss of glycemic control observed by either 1) an increase from baseline in HbA1c values by 1.0% or more that is confirmed at a subsequent clinic visit scheduled at the Investigator's discretion, or 2) fasting glucose value ≥ 250 mg/dL or random blood glucose > 300 mg/dL for 4 days during a 7-day period measured by home self-monitored blood glucose (SMBG), and confirmed by fasting or random glucose test within the same range of values (measured by local laboratory) at a clinic visit, will result in initiation of rescue medication. A clinic visit to confirm the values obtained by home SMBG or fasting/random glucose tests must take place within 2 weeks following the aforementioned self-measurements.

Patients meeting rescue criteria will be treated with antihyperglycemic therapy (e.g., insulin) by the Investigator or referred to their treating physician to seek conventional antihyperglycemic intervention. Patients meeting these criteria should remain in the study and continue to receive study medication, at the discretion of the Investigator. Acute decompensation due to an intercurrent illness treated briefly with insulin will be allowed for 2 weeks, if longer this should be considered as rescue medication.

Derivation of variables at initiation of rescue medication

Efficacy

In general, efficacy data are to be continuously collected during the glycemic rescue therapy. For all efficacy endpoints, except the plasma exenatide concentration endpoint, data collected after the first administration of rescue therapy will be excluded from the descriptive statistical summary and inferential statistical analyses.

However, data collected after initiation of rescue medication will be included in several sensitivity and supportive analyses for the primary analysis to provide a comprehensive view of the treatment effect (see more details in Section 4.2.3.4).

Safety

Because patients can continuously receive study medication concurrent with the rescue therapy, all safety data collected during the rescue medication treatment period will be summarized and analyzed together with those collected prior to the rescue therapy.

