Appendix E
Extended Safety Follow-Up Period

1. Overview and Rationale

In response to a request from the European Medicines Agency Committee, patients participating in Study BCB114 will be observed in an Extended Safety Follow-Up Period following discontinuation of study medication administration. Long-term follow-up of pediatric patients participating in Study BCB114 will allow observation of ongoing development and growth on an individual patient basis and a description of the occurrence of selected adverse events in pediatric patients in the absence of EQW treatment following up to 52 weeks of EQW administration.

2. Objective

The objectives of this Extended Safety Follow-Up Period are:

- To describe safety parameters over time following discontinuation of study medication administration, including the following:
 - Adverse events (AEs) of special interest
 - Ongoing prescription medications
 - Height and weight
 - Tanner pubertal stage
 - Carcinoembryonic antigen (CEA) concentration
 - Calcitonin concentration

3. Study Design

Following discontinuation of study medication administration, patients with a height increase of at least 5 mm between Visit 8 (Week 28) and Visit 11 (Week 62/Study Termination) will enter the Extended Safety Follow-Up Period. Patients who discontinue study medication administration prior to Visit 10 (Week 52/Study Termination) will also enter the Extended Safety Follow-Up Period, unless they have a height increase of less than 5 mm over a 6-month interval at study-site visits prior to discontinuation of study medication. Patients who do not have height assessments at study-site visits over a 6-month interval prior to discontinuation of study medication will enter the Extended Safety Follow-Up Period.

During the Extended Safety Follow-Up Period, patients will return to the study site at approximately 6-month intervals for a period of up to 3 years or until the difference between 2 height measurements over a 6-month interval is less than a 5 mm increase (whichever comes first). During the Extended Safety Follow-Up period, adverse events of special interest (AESIs) (see [Table 1](#)), and ongoing prescription medication will be reviewed, height, weight, and Tanner pubertal stage will be assessed, and CEA and calcitonin concentrations will be measured.

4. Visit Structure

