3.3 Exploratory efficacy variables

The exploratory efficacy endpoints are:

- Change in Body Mass Index (BMI) from baseline Visit 2 (Week 0) to Visit 7 (Week 24), Visit 10 (Week 52), and to each intermediate visit as applicable
- Change in body weight percentile and height percentile from baseline Visit 2 (Week 0) to Visit 7 (Week 24), Visit 10 (Week 52), and to each intermediate visit as applicable. The height and weight percentile will be determined based on the standardized growth chart for boys and girls (developed by the National Center for Health Statistics in collaboration with the National Center for Chronic Disease Prevention and Health Promotion).

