A MMRM modeling approach will be implemented to compare changes in body weight percentile, and height percentile between treatment groups from Visit 2 (Week 0) to Week 24, and each intermediate visit.

The least squares mean (LSM) change from baseline and SE bar by visit will be presented in figures by treatment group. The p-value for the difference between treatment groups by visit will also be provided in the figure.

The observed values and change from baseline for body weight percentile and height percentile will be summarized by visit using descriptive statistics (mean, median, standard deviation, minimum, maximum). This will be provided separately for both the Evaluable analysis set during the controlled assessment period and for the subset of Evaluable patients who received open-label EQW during the extension period for the Treatment period.

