4.2.4 Safety and tolerability analysis

Analysis of safety data will be performed using the Safety analysis set. All safety and tolerability variables such as examination of AEs, clinical laboratory measurements, physical examination findings, vital signs, and antibodies to exenatide will be summarized descriptively by treatment groups. Observations post-rescue will be included for safety analyses.

For all safety endpoints summary tables will be presented by visit to Week 52, and where applicable also for the 10-week follow-up, for each treatment group. Continuous variables (observed, change from baseline, laboratory and vital signs parameters) will be summarized by visit using number, mean, median, standard deviation, minimum and maximum for each

treatment group. Categorical variables (incidence of AEs, antibodies, physical examination, Tanner pubertal stage) will be summarized by visit in the form of number and percentage (%) for each treatment group.

A listing of Tanner pubertal stage data will also be provided.

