CSP Section 12.6.1 states that last observation carried forward will be used for missing data at endpoint for proportion of patients meeting HbA1c goals of $\leq 6.5\%$ and $< 7.0\%$, however, patients with missing HbA1c at endpoint will be considered as non-responders. Additionally, the logistic regression sensitivity analysis described in the CSP has been replaced with a more appropriate CMH analysis using MI pattern mixture model imputation (Sections 4.2.3.4 and 4.2.3.5), as this tests the robustness of the results from the main analysis by altering the missing data assumption.

CSP Section 12.6.1 stipulates ‘The analyses of all other efficacy endpoints will be performed in ITT population.’ Upon review of the endpoints it was agreed that all endpoints related to HbA1c should be evaluated using the Evaluable analysis set.

CSP Section 12.6.1 outlines a MMRM method will be implemented for the secondary efficacy endpoint, lipids. It was agreed after blinded data review that the data could be sufficiently reviewed as summary statistics.

CSP Section 12.6.2 specifies that both baseline HbA1c and HbA1c strata will be included in the MMRM model for the primary analysis. However, these variables will be highly correlated resulting in multicollinearity in the statistical model. Therefore, HbA1c strata will not be included in the primary model. For secondary and exploratory MMRM analyses, screening HbA1c strata will be used in the model instead of continuous baseline HbA1c.

The sensitivity and supportive analyses in Section 4.2.3.4 were not specified in the CSP and have been added to further support the primary analysis and to examine the influence of missing data due to drop-out and/or receiving rescue therapy.

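### Heights after rescue drop out of the SAP's only post-baseline summary of linear growth, and the analysis set for that summary conflicts with the protocol

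*SAP*

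**What the plan says.** - **Class of endpoint.** SAP 3.3 opens with "The exploratory efficacy endpoints are" and lists BMI, body weight percentile and height percentile, each to Week 24, Week 52 and the visits between.
- **Rescue rule for efficacy.** SAP 4.1.4 states that "data collected after the first administration of rescue therapy will be excluded from the descriptive statistical summary and inferential statistical analyses". The rule covers all efficacy endpoints; plasma exenatide concentration is the one exception.
- **Rescue rule for safety.** SAP 4.1.4 keeps all safety data from the rescue period, giving as its reason that study medication can continue alongside rescue. SAP 4.2.4 repeats this: "Observations post-rescue will be included for safety analyses".
- **Analysis set.** SAP 4.2.3.6 begins by placing exploratory endpoints in ITT, subject to stated exceptions, and names height percentile among the variables to be summarised. At its end it says of the body weight and height percentile summaries: "This will be provided separately for both the Evaluable analysis set during the controlled assessment period and for the subset of Evaluable patients". That subset is those dosed with EQW in the extension.
- **Listed departures.** On analysis sets for efficacy endpoints, SAP 5 says only that "it was agreed that all endpoints related to HbA1c should be evaluated using the Evaluable analysis set".
- **Protocol.** Section 12.2.3 lists height percentile as an exploratory endpoint. Section 12.6.4 puts exploratory endpoints in ITT. Section 12.6.1 applies the rescue cut to the efficacy analysis used for inference. Height measurement is standardised in 6.4.6, within the Safety section. Appendix E includes height and weight under the objective "To describe safety parameters over time following discontinuation of study medication administration, including the following".

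**The concern.** Linear growth in children and adolescents on EQW is something the sponsor wants to watch: patients who are still growing are followed for up to 3 years after treatment. Within this SAP, height percentile is the only summary that addresses it after baseline. Because the endpoint carries the efficacy label, it inherits a rule written for glycemic endpoints, where rescue medication directly contaminates the measurement. The SAP's own reason for keeping post-rescue safety data, continued exposure to study medication, applies equally to height.

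Rescue is a post-randomisation event that the treatment is meant to influence. A descriptive table that cuts heights at rescue shows, at each later visit, only patients not yet rescued, and no model compensates for that. The conflict over the analysis set also means that the table and the MMRM can rest on different patients.

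**Working it through.** The plan gives no figure to reproduce here, so this is mainly a comparison of texts.

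**1. Does the rescue rule reach the descriptive summary of height percentile?** Yes. SAP 3.3 makes it an efficacy endpoint, SAP 4.1.4 covers all efficacy endpoints but one, and it names descriptive as well as inferential results. Height is not excepted.

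**2. Does a safety summary bring the later heights back?** No. The vital-sign tables in SAP 4.2.4.5 cover systolic and diastolic blood pressure and heart rate only.

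**3. Is growth otherwise covered?** In part. Tanner stage, IGF-1 and the other growth and development hormones, and the bone turnover markers are safety variables (SAP 3.4, 3.5, 4.2.4.4), so post-rescue values are kept. Weight percentile, BMI and BMI percentile are also planned (SAP 4.2.3.6). None of these summarises height.

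**4. Does the protocol require the cut?** For the model, yes: protocol 12.6.4 uses the MMRM approach of 12.6.3, which stops at rescue. For the descriptive summary, no: protocol 12.6.1 ties the cut to inference. The extension is not among the changes in SAP 5.

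**5. Has the SAP done otherwise for a comparable variable?** Yes. For eGFR, SAP 4.2.4.4 plans the analysis both without and with post-rescue data, in the Safety set.

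**6. Which analysis set?**

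| Source | Set for height percentile |
|---|---|
| Protocol 12.6.4 | ITT |
| SAP 4.2.3.6, opening | ITT, subject to stated exceptions |
| SAP 4.2.3.6, MMRM | none named, so ITT by default |
| SAP 4.2.3.6, descriptive summary | Evaluable |
| SAP 5 | moves only HbA1c-related endpoints to Evaluable |

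Evaluable requires a baseline and a post-baseline HbA1c (SAP 2.1.4). Protocol 6.2.3 schedules HbA1c and height together at each of Visits 3 to 10, so a patient with a post-baseline height on treatment will nearly always have an HbA1c from the same visit. The set matters for consistency; it will remove almost nobody.

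**7. Size of the rescue exclusion.** The documents give no rescue rate. With 77 randomised 5:2, the arms are 77 × 5/7 = 55 and 77 × 2/7 = 22. The shares below are assumptions, applied equally to both arms:

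| Assumed share rescued | EQW (of 55) | Placebo (of 22) | Total (of 77) |
|---|---|---|---|
| 5% | 2.8 | 1.1 | 3.9 |
| 10% | 5.5 | 2.2 | 7.7 |
| 20% | 11.0 | 4.4 | 15.4 |
| 30% | 16.5 | 6.6 | 23.1 |

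These are patients who lose later heights, not all heights. Someone rescued between Weeks 12 and 18 keeps Weeks 4, 8 and 12 and loses Weeks 18, 24, 28, 40 and 52. SAP 5 describes the number rescued at Week 24 as low, so the lower rows are more plausible for the controlled period. Nothing in the documents indicates which row fits Week 52.

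**The case against.** The classification largely follows the protocol, which lists height percentile as exploratory and apart from its safety and exploratory safety endpoints (12.2.3 to 12.2.5). Appendix E calls height a safety parameter as an objective of the extended follow-up, which SAP 1 places outside its scope. The heights are not lost to reporting: SAP 4.1.1 promises individual listings, and Appendix E requires patient profiles spanning treatment and follow-up for those who enter that period, with no rescue exclusion stated. Rescue by Week 24 was low. The Evaluable restriction is, on its words, an exception that the section's opening permits.

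Most of this stands, and it keeps the point small. It does not explain why the rule was extended to descriptive summaries without being recorded. Nor do listings or profiles replace a by-arm summary: Appendix E says that no descriptive summaries will be prepared for the extended follow-up. An exception permitted by the SAP's wording is still a departure from protocol 12.6.4 that SAP 5 omits.

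A reader might infer more than the documents support:
- **That the SAP has no other growth result.** It has several, and the safety ones keep post-rescue data.
- **That growth is assessed only in patients who kept glycemic control.** Rescued patients contribute every height up to rescue.
- **That a 52-week comparison with placebo is distorted.** The MMRM stops at Week 24, and everyone in the extension receives EQW.
- **That rescue rates by arm can be used to size a bias, or that poor control itself affects growth.** The documents support neither, and the point needs neither.

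**Conclusion.** The point holds as a modest one. As written, heights after first rescue are left out of both the descriptive summary and the MMRM of height percentile, and no other summary table shows them. The exclusion from the model has protocol support; the exclusion from the descriptive summary does not, and it is not listed as a change. The Evaluable set for the descriptive summary conflicts with the protocol and with the opening of the same SAP section.

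The effect is probably small to Week 24 and unknown to Week 52. The range of about 4 to 23 affected patients rests wholly on assumed rescue shares of 5% to 30%. The primary analysis, the testing hierarchy and the planned safety tables are untouched. A reader might conclude that height percentile must be reclassified as a safety endpoint. That is not needed: an added summary answers the growth question without changing the protocol's exploratory class.

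**What to change.** 1. Keep the exploratory MMRM of height percentile as planned.
2. Add to SAP 4.2.4 a by-visit descriptive summary, by treatment group, of observed values and change from baseline in height percentile. Use the Safety set and all observed heights, including those after rescue.
3. State explicitly that heights at the Early Termination and Week 62 visits are included. Placing the table under safety does not settle this: SAP 4.1.3.4 excludes data after study medication stops, and the safety treatment period in SAP 3.6.5.2 generally ends 7 days after the last dose.
4. In SAP 4.2.3.6, change the set for the body weight and height percentile summaries from Evaluable to ITT, or list the departure in SAP 5.

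The cost is one extra table and some SAP wording. Height is already measured at every study-site visit, so no new data are needed.
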